1.3 Exclusion criteria

1.3.1 Exclusion criteria for COPD

(1) Patients who fail to meet the diagnostic criteria for COPD, or COPD patients in the phase of acute exacerbation;

(2) Patients have the following complications, such as pneumonia, bronchial asthma, bronchiectasis, active tuberculosis, pneumothorax, chest trauma, tumors of the lung or thorax;

(3) Patients have concomitant conditions of heart diseases, such as chronic stable angina pectoris (CSAP);

(4) Patients have serious concomitant conditions and fail to treat them effectively, such as diseases of the digestive, urinary, respiratory, hematological, and nervous

system;

(5) Patients have mental illness, severe depression, alcohol dependence or history of drug abuse;

(6) Pregnant or lactating patients;

(7) Patients are participating in other trials.

1.3.2 Exclusion criteria of health volunteers

(1) Participants have mental illness, severe depression, alcohol dependence or history of drug abuse;

(2) Pregnant or lactating participants ;

(3) Participants are participating in other trials.

1.4 Participant recruitment

All the participants will be enrolled from the Third affiliated hospital of Zhejiang Chinese Medical university and the First affiliated hospital of Zhejiang Chinese Medical university.

2. Study methods

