2.1 Study design

This is a prospective and open-label clinical trial. The time frame of the trial ranges from July 2019 to December 2020. A total of 120 participants will be divided into the healthy control group, COPD group and healthy intervention group., with 40 in each group respectively.

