2.2 Sample size estimation

This project is a clinical research using laser doppler to assess the biological characteristics of this meridian phenomenon. It belongs to meridian researches. Compared with general clinical trials, there is no unified standard for the sample size estimation. Based on similar studies conducted in China and foreign countries, as well as the consideration of the actual research conditions of this study, we planned to enroll a total of 120 participants, which includes 40 COPD patients and 80 healthy volunteers.

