2.4 Grouping

A total of 120 participants will be divided into the healthy control group, COPD group and healthy intervention group., with 40 in each group respectively.

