2.3 Statistical analysis

All data in this study will be analyzed by a blinded statistician. Independent sample T test and Chi-square test (χ^2 test) will be used for numerical variables and categorical variables, respectively. When the distribution of variables is abnormal, a non-parametric test will be selected. A P value < 0.05 will be considered statistically significance.

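### Two hospitals recruit over 18 months with no rule that each enrols COPD patients and healthy controls in similar proportions and over the same period, and the planned comparison has no hospital term

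*Combined protocol and SAP*

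**What the plan says.** Part 2, section 1.4, names the recruiting sites: "All the participants will be enrolled from the Third affiliated hospital of Zhejiang Chinese Medical university and the First affiliated hospital". Section 2.1 gives the calendar: "The time frame of the trial ranges from July 2019 to December 2020", which is 18 months. The only grouping rule is in section 2.4: "A total of 120 participants will be divided into the healthy control group, COPD group and healthy intervention group., with 40 in each group respectively". No section gives numbers per hospital by group, matching, concurrent or interleaved enrolment, or a spread of operators across groups.

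SAP 2.3 gives the analysis: "Independent sample T test and Chi-square test (χ^2 test) will be used for numerical variables and categorical variables, respectively", with an unspecified non-parametric test when the distribution is not normal. There is no term for hospital, operator or date. The SAP does not list its contrasts. COPD versus healthy control is the one implied by section 2.6.3, where both groups are recorded at the same four acupoints.

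Several safeguards bear on measurement:
- same-day limits on drinks, smoking, food and exercise (2.6);
- control of room temperature, humidity, sunlight and air movement (2.6.2);
- 15 minutes of supine rest (2.6.3);
- an examination SOP, staff training, data checks and three-monthly supervision of operators (section 6).

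Outcome assessors are not blinded (2.5).

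**The concern.** COPD status cannot be randomised, so the COPD versus control contrast depends on the two groups being recruited and recorded under the same conditions. They come through different streams. Patients need stable, spirometry-confirmed GOLD 2 or 3 disease, while volunteers need a recent medical report showing no disease. Nothing makes the two streams run side by side at each hospital. The plan would be followed to the letter if most COPD patients came from one hospital and most controls from the other, or if one group were completed months before the other.

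PU is a primary outcome. If PU differs between hospitals or periods for reasons other than COPD, part of that difference is added to the group contrast, and the planned test cannot remove it. If hospital and group coincide completely, no later model can separate them.

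**Working it through.** **The plan's own figure.** The total of 120 (3 × 40) cannot be reproduced. Section 2.2 argues that "there is no unified standard for the sample size estimation" and gives no effect size, SD or power. For scale, with 40 per group and two-sided α = 0.05, the detectable difference is (1.960 + 0.842) × √(2/40) = 0.63 SD at 80% power and (1.960 + 1.282) × √(2/40) = 0.72 SD at 90%.

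**Inputs from the documents.** 40 COPD patients and 40 healthy controls (2.4); unadjusted independent-sample t test and a 0.05 threshold (SAP 2.3). The SAP does not state sidedness; two-sided is assumed.

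**Assumed inputs.** The shift in PU between hospitals, 0.2 to 0.8 within-hospital SD, and the split of each group between hospitals. The documents give neither.

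**Formula.** Bias = (share of COPD patients at hospital A − share of controls at hospital A) × shift. For example, a 75/25 versus 25/75 split with a 0.5 SD shift gives (0.75 − 0.25) × 0.5 = 0.25 SD.

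**False-positive rate.** This is the chance that the planned t test gives p < 0.05 at one acupoint when COPD has no effect on PU. It was simulated with 40,000 runs per scenario. Each cell shows bias in SD, then the rate.

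| Split, COPD vs control | Shift 0.2 | Shift 0.3 | Shift 0.5 | Shift 0.8 |
|---|---|---|---|---|
| 50/50 vs 50/50 | 0; 4.9% | 0; 4.6% | 0; 4.4% | 0; 3.4% |
| 65/35 vs 35/65 | 0.06; 5.8% | 0.09; 6.6% | 0.15; 9.0% | 0.24; 15.2% |
| 75/25 vs 25/75 | 0.10; 7.4% | 0.15; 9.8% | 0.25; 18.2% | 0.40; 37.8% |
| 100/0 vs 0/100 | 0.20; 14.1% | 0.30; 26.4% | 0.50; 60.0% | 0.80; 94.4% |

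**Check.** The t-test calculation without simulation, with within-group variance held at 1, gives 59.8% at a bias of 0.50 SD and 19.7% at 0.25 SD. The simulated 18.2% is slightly lower because mixing two hospitals within a group widens that group's spread.

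With equal shares the rate falls below 5% for the same reason: the hospital difference inflates the error variance but not the group difference. A hospital term would remove that inflation.

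**The case against.** The strongest reply is that recruitment is not measurement. Section 1.4 says where people are enrolled, not where they are recorded, and sections 2.6.2 and 2.6.3 speak of one flowmeter and one room. That fits a single recording station at least as well as two. This stands: a reader might infer that two devices and two rooms are in use, and the documents do not support it. With one station the device and room route disappears. Recruitment source, calendar time and operator remain.

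The safeguards also act on the season and operator differences in question, and software calculates PU. This stands in part. They should shrink any shift, so it would be wrong to say that such differences pass straight into the contrast. They do not balance the groups, and they do not change whom each hospital recruits.

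The size is assumed. At shifts of 0.2 to 0.3 SD, a 65/35 versus 35/65 split gives only 5.8% to 6.6%, and a 75/25 versus 25/75 split only 7.4% to 9.8%. This stands: rates of 20% to 60% need a shift of about 0.5 SD together with severe or complete separation, and nothing in the documents points to either.

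Nor is hospital balance the main protection for this contrast. Eligible ages differ (35 to 75 for COPD, 20 or over for volunteers), and patients keep their treatment while volunteers take no medication (2.6.4). Balancing hospitals corrects neither.

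Finally, four sites are recorded at once in each person. A shift common to all four would largely cancel in a within-person Lung versus Heart contrast, which serves the site-specificity aim. The moxibustion comparisons between sessions in the same people are likewise much less exposed.

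**Conclusion.** The gap is certain. Neither the recruitment rules nor the analysis protects the between-group PU contrast against an uneven mix of hospitals or calendar time. Its effect is possible rather than shown. If hospitals differ by 0.2 to 0.8 SD, the false-positive rate per acupoint runs from about 7% to 38% at a 75/25 versus 25/75 split and from 14% to 94% with complete separation, against 3.4% to 4.9% with equal shares. Those ranges rest on an assumed shift, an assumed split, a two-sided test and no true COPD effect.

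A reader might go further and conclude that the contrast is already confounded by hospital. The documents do not show this: they give no split by hospital and no place of recording, and they contain real, if partial, measurement controls. The point is a cheap improvement to the plan, limited to the COPD versus control comparison.

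**What to change.** **Protocol 1.4 and 2.4.** Require each hospital to enrol COPD patients and healthy controls concurrently and in similar proportions. Have the operators in use record both groups. Log hospital, operator and date for every recording. State whether recording takes place at one hospital or both.

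**SAP 2.3.** Compare COPD with control PU in a linear model with group and hospital. If PU is not normally distributed, use a hospital-stratified rank test such as van Elteren's. The hospital term does not cover season or operator; concurrent enrolment and shared operators handle those by design, and the log lets the balance be checked. Adjustment works only if both groups are present at each hospital, so the recruitment rule matters more than the model term.

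**Cost.** Less freedom to recruit wherever is quickest, some scheduling, a log and one degree of freedom. The sample size does not change, and no patients, staff or equipment are added.

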2.1 Study design

This is a prospective and open-label clinical trial. The time frame of the trial ranges from July 2019 to December 2020. A total of 120 participants will be divided into the healthy control group, COPD group and healthy intervention group., with 40 in each group respectively.

2.2 Sample size estimation

This project is a clinical research using laser doppler to assess the biological characteristics of this meridian phenomenon. It belongs to meridian researches. Compared with general clinical trials, there is no unified standard for the sample size estimation. Based on similar studies conducted in China and foreign countries, as well as the consideration of the actual research conditions of this study, we planned to enroll a total of 120 participants, which includes 40 COPD patients and 80 healthy volunteers.

2.3 Participant selection

Prior to the study, the researchers should explain the purpose, contents, benefits

and potential risks of the study to all participants clearly and colloquially. Then the participants or their families should sign the informed consent form, otherwise, they will not be included in the trial.

After signing the informed consent form, all participants will receive the following assessment to determine whether they could be included.

- (1) Demographic data and medical history;
- (2) Vital signs: respiratory rate, heart rate, blood pressure, and body temperature;
- (3) Laboratory examinations: blood routine test, biochemical routine test (including AST, ALT, BUN, Cr, GLU, blood lipid, etc.);
- (4) Electrocardiogram.

2.4 Grouping

A total of 120 participants will be divided into the healthy control group, COPD group and healthy intervention group., with 40 in each group respectively.

2.5 Blinding

The participants and outcome assessors will not be blinded. In the data analysis stage, blinded statistical analysis will be adopted. Statistical analysis will be conducted by third party statisticians who are blinded to the study protocol.

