2.6.3 Procedures for LDF examination and moxibustion intervention

A four-channel LDF (PeriFlux System 5000, Sweden) will be used to measure the microcirculatory characteristics of meridian phenomena for the Heart and Lung meridians, which could monitor 4 measuring sites simultaneously. The participants will be asked to stabilize for 15 minutes in a supine position in the experimental room before formal examination. They will be informed to keep silent and normal breath and avoid limb movement during the whole measuring period. The probes will be left at relevant measuring sites. Blood flow curve will be recorded constantly using Perisoft software (PeriFlux, Sweden). Perfusion units (PU) of microcirculatory flux in the measuring sites will be calculated by the software [PU = concentration of moving blood cells (CMBC) × velocity (V)].

(1) Healthy control group and COPD group

The probes will be left at 4 measuring acupoints, which include Shenmen (HT7) and Shaohai (HT3) of the Heart meridian, Taiyuan (LU9) and Chize (LU5) of the Lung meridian. The blood flow curve and PU will be recorded for 5 minutes.

(2) Healthy intervention group

Two sessions of moxibustion intervention will be performed in the Heart meridian and Lung meridian successively. The washout period between the two sessions is at least one day.

1) Intervention in the Heart meridian: By igniting the moxa stick and inserting it into a homemade moxibustion holder to adjust the appropriate angle and height, moxibustion will be performed above Shaohai (HT3) of Heart meridian for 15 minutes. During moxibustion, the probes will detect the blood flow curve and PU in four sites in two meridians, which include Shaohai (HT3) of the Heart meridian, the midpoint of the Heart meridian along the left forearm (i.e. the midpoint of the line

between HT3 and HT7), Chize (LU5) of the Lung meridian, and the midpoint of the Lung meridian along the left forearm(i.e. the midpoint of the line between LU5 and LU9). The measuring time points include 5 minutes before moxibustion, 15 minutes during moxibustion and 5 minutes after stopping moxibustion.

2)Intervention in the Lung meridian: The moxibustion acupoint is Chize (LU5) of the Lung meridian. The LDF examination, moxibustion procedure, measuring sites and time points are the same as 1).

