2.6.4 Concomitant treatments

During the study period, all the participants in the COPD group will maintain their previous treatment regimen. If additional medications or other treatments are used during the study period due to any reasons, the details (e.g. the name, administration time and dosage of the medication) should be documented.

Besides, participants in the healthy control group and healthy intervention group should not take any medications during the full study period. If drugs or other treatments are adopted due to sudden diseases, relevant information should be documented and researchers will evaluate whether they should be withdrawn from the study.

3. Outcome measurement

Primary outcomes will be blood flow curve and blood perfusion units (PU) of relevant sites along the Heart and Lung meridians.

4. Safety evaluation

Adverse events (AEs) that occur during the trial will be recorded and assessed by the investigators during each examination session and at each visit next time. If serious AEs occur, the researchers should report them to the principal investigator and ethics committee immediately, who will make a decision on whether the participant should be withdrawn from the study.

5. Ethical approval and study registration

Ethics approval (approval document No: ZCMU-KY-2019-042, April 29, 2019) was obtained from the Ethics Committee of Zhejiang Chinese Medical University. The purpose, contents and potential risks of the research will be fully explained to the

participants and their families. All participants will complete the informed consent form before participating in the study. All participants' personal and disease information will be kept confidential.

6. Quality control

(1) The trial protocol has been modified according to suggestions from experienced acupuncturists.

(2) Before the trial, all researchers who enroll participants and collect data must attend a series of training sessions. These training sessions will ensure that all research staff involved fully understand the trial protocol and standard operating procedures (SOP).

[figure not shown]
(3) SOP of the examination method is designed before the trial.

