(4) Data collection will be performed in accordance with the pre-approved protocols. All assessors will be trained uniformly to record outcomes and fill in the case report forms. One independent supervisor will regularly verify the consistency of the raw data and the recorded data. Data management and monitoring will also be performed by using ResMan Research Manager (<http://www.medresman.org>).

(5) During the trial, clinical supervisors will guide and supervise the operators regularly (once every three months).

(6) Economic compensation is adopted to improve compliance and reduce dropouts and withdrawals of participants.

7. Flow diagram of the study design

Part3. Statistical Analysis Plan

1. Data entry and storage

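### Outcome assessors are unblinded without exception, although the recorded LDF traces could be coded before the blood flow curve is read and before any artefact or averaging choice is made

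*Combined protocol and SAP*

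**What the plan says.** Protocol section 2.5 (Blinding) states "The participants and outcome assessors will not be blinded". Masking begins later: "In the data analysis stage, blinded statistical analysis will be adopted", carried out by third-party statisticians. SAP section 2.3 repeats that the statistician is blinded.

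Section 3 (Outcome measurement) has two components: "Primary outcomes will be blood flow curve and blood perfusion units (PU) of relevant sites along the Heart and Lung meridians". It gives no summary measure, scoring rule or time point for either.

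Section 2.6.3 has the curve recorded continuously in the device software, and "Perfusion units (PU) of microcirculatory flux in the measuring sites will be calculated by the software". For the healthy control and COPD groups, "The blood flow curve and PU will be recorded for 5 minutes" at the same four acupoints. In the healthy intervention group, each session is recorded for 5 minutes before, 15 minutes during and 5 minutes after moxibustion.

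Section 6 (Quality control) says "All assessors will be trained uniformly to record outcomes and fill in the case report forms", and has an independent supervisor regularly compare raw with recorded data.

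**The concern.** The operator who places probes or applies moxibustion cannot be masked. Reading the resulting trace is a separate task, and because the trace is held in software it can be done later from a file that does not show the group. Section 2.5 does not separate the two tasks, so whoever reads a curve may know whose curve it is and which site it comes from.

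Masking the statistician does not compensate. Any influence on how a curve is scored, which stretch is treated as artefact or which minutes are averaged is already in the numbers that the statistician receives. At stake is the credibility of the COPD versus healthy control comparison and of the site-specificity question in the study objectives, because both depend on differences between traces whose labels the reader knows.

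**Working it through.** **1. Who is masked, and at which step**

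| Step | Source | Masked? |
|---|---|---|
| Probe placement, moxibustion, recording | 2.6.3 | No; not feasible for the operator |
| PU calculation | 2.6.3 | Done by software |
| Curve reading, artefact handling, choice of averaging window | No rule given | No masking provided for (2.5) |
| Recording outcomes on the case report form | 6(4) | No (2.5) |
| Check of raw against recorded data | 6(4) | Not stated |
| Statistical analysis | 2.5; SAP 2.3 | Yes |

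The third row is the gap. The documents do not say how a curve is scored, whether the whole recording or part of it gives the PU value, how the 15 minutes of moxibustion are summarised, or what is done with movement artefacts. Section 2.6.3 asks participants to keep their limbs still, so movement is a recognised problem, but no handling rule follows.

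**2. Could the files be masked?**

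- COPD versus healthy control: same four acupoints, same 5-minute recording. Coded files would have the same format and length.
- Heart versus Lung moxibustion session: same measuring sites and periods, so files can be coded, but a rise in the heated channel may reveal which session it is.
- Intervention group versus the other two: 5 + 15 + 5 = 25 minutes against 5 minutes, so length alone identifies the group.

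**3. Size, as an illustration only**

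The plan has no figure to reproduce: section 2.2 gives no effect size, SD or power.

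Inputs from the documents: n = 40 per group (2.1), significance level 0.05 and independent-samples t test (SAP 2.3). Assumptions: a two-sided test (the SAP does not say), no true difference, and a reading bias that shifts one group's mean by d SD.

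Non-centrality: λ = d × √(n/2) = d × √20 = 4.472 d. Degrees of freedom: 40 + 40 − 2 = 78; critical value 1.991. False-positive rate = P(|T| > 1.991), where T is non-central t with parameter λ.

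| Assumed d (SD) | λ | False-positive rate per comparison |
|---|---|---|
| 0 | 0 | 5.0% |
| 0.1 | 0.447 | 7.3% |
| 0.2 | 0.894 | 14.3% |
| 0.3 | 1.342 | 26.3% |

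A normal approximation gives 7.3%, 14.5% and 26.9% for the last three rows, so the result does not depend on the method. The documents do not say which value of d applies. If PU is simply the software average over the whole recording, d from this source could be zero for PU.

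**The case against.** The strongest reply is that the plan describes no human step in producing PU. Section 2.6.3 has the software calculate PU, speaks of curve and PU being recorded together, and fixes the recording periods. The whole 5-minute average may already be what is meant. The supervisor's check also covers errors in carrying PU to the case report form. All of this stands, and it makes the risk for PU clearly smaller than for the curve. It does not close the gap: fixed periods say what is recorded, not what is summarised, and the supervisor's check is not stated to be masked or to cover scoring or artefact decisions.

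A reader might infer three stronger things that the documents do not support:

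- That both primary outcomes pass through an unmasked choice of segments. No such step is described; it is only possible because no rule excludes it.
- That the false-positive rate is 14% to 26%. Those values follow from an assumed shift of 0.2 to 0.3 SD in a consistent direction. The plan states no expected direction for PU in COPD, and the range must start at zero bias and 5%.
- That a Lung-versus-Heart comparison within persons would be corrupted. SAP section 2.3 names only independent-samples t, chi-square and unspecified non-parametric tests, so no such analysis is set out.

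It is also fair to say that fixed windows and an artefact rule are matters of outcome definition, and would remove most discretion over PU without any masking. Masking still matters for reading the curve and marking artefacts.

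**Conclusion.** The point holds in a limited, conditional form. Section 2.5 leaves all outcome assessment unmasked when part of it could be masked at little cost, and blinding the statistician comes too late to help. The exposure is mainly the reading of the blood flow curve, a primary outcome without a scoring rule, plus any artefact removal or averaging-window choice.

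This is a risk of bias, not evidence of bias, and its size cannot be derived from the documents: about 5% to 26% false positives per comparison for assumed shifts of 0 to 0.3 SD. The conclusion assumes that traces can be exported or renamed without labels, which the use of recording software suggests but the documents do not state. The change should be made. Confidence is moderate, because the plan may intend a whole-window software mean for PU.

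**What to change.** **Section 2.5.** Replace the blanket statement with two parts. Participants, and the operators who place probes and give moxibustion, are not blinded. Curve reading, artefact marking and any PU extraction are done on files renamed with a random code, with group, session and channel labels removed, by one of the already trained assessors who did not run that recording.

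**Section 2.6.3.** State that PU is the software mean over the whole 5-minute resting window and, in the moxibustion sessions, over minute blocks fixed in advance. State that artefacts are marked on the coded file before unmasking.

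**Cost.** Minor administrative work: coding files, keeping the code list and dividing tasks. Section 6 refers to assessors in the plural, so the split looks feasible, although staffing numbers are not given. No additional participants, visits or equipment are needed.

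**Limits.** Masking is workable for COPD versus healthy control. It is only partial for moxibustion, where the heated channel and the 25-minute recording can be recognised. It does nothing about unblinded probe placement and acquisition, which should be acknowledged as a remaining limitation.

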1.1 Data entry

(1) The original data collection

All observation scales will be measured on a "one to one" basis according to the unified standard, and the subject will be completed independently under the guidance of the investigators to ensure complete and correct completion. In the spot, check whether the filling quantity is accurate. If any omission or blurring is found in the case report forms, the assessors should verify the original data in time.

(2) Data entry and statistics

The Excel spreadsheet is used to record the original data and ensure it is accurate and reliable. A blinded statistician is employed to carry out the statistical analysis and the research managers should verify whether the statistical methods are appropriate.

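### Section 2.5 blinds the statistician to the study protocol and never masks group identity, so it hides neither COPD nor control status and does not assure the analyst of knowing which records are paired

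*Combined protocol and SAP*

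**What the plan says.** Protocol section 2.5 leaves participants and outcome assessors unblinded. It then promises masking at the analysis stage, "In the data analysis stage, blinded statistical analysis will be adopted", and defines it in the next sentence: "Statistical analysis will be conducted by third party statisticians who are blinded to the study protocol". The SAP (Part 3) adds only that "All data in this study will be analyzed by a blinded statistician" (section 2.3), and section 1.1 also refers to a blinded statistician. Neither SAP section says what is hidden. No section describes coded groups, a code holder or a time of unmasking.

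The data structure is set out only in protocol section 2.6.3. The flowmeter is one "which could monitor 4 measuring sites simultaneously". In the healthy intervention group, "Two sessions of moxibustion intervention will be performed in the Heart meridian and Lung meridian successively", and within each session "The measuring time points include 5 minutes before moxibustion, 15 minutes during moxibustion and 5 minutes after stopping moxibustion". The heated point differs between sessions (HT3, then LU5). The COPD and healthy control groups each have a single 5-minute recording at four acupoints.

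The SAP mentions none of this. Its section 2.3 states: "Independent sample T test and Chi-square test (χ^2 test) will be used for numerical variables and categorical variables, respectively", with an unspecified non-parametric test as the fallback. Section 1.1 adds a check: "the research managers should verify whether the statistical methods are appropriate".

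**The concern.** Blinding an analyst normally means concealing which code is which group, so that data handling and model choices cannot be steered towards a result. The sentence in 2.5 conceals something else. It does not hide who has COPD and who is a control, and it keeps from the analyst the information needed to see that many records come from the same person.

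Two things are at stake. First, the trial has no stated protection against analyst bias in the COPD-versus-control comparison, although masking there would be easy: both groups have the same four sites and the same recording length. Second, the moxibustion questions are within-person questions (before against during, heated meridian against the other, one session against the other). An analyst without the design, working from a SAP that names only independent-sample tests, may treat paired records as unpaired.

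**Working it through.** The plan states no figure on this point. Protocol section 2.2 gives no effect size, standard deviation or power, so there is no calculation of the plan's own to reproduce. The check is a reading of the text, then an illustration of size.

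**Text**

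| Question | Where answered | Answer |
|---|---|---|
| What is hidden from the analyst? | Protocol 2.5 | The study protocol |
| Are group labels masked or coded? | Nowhere | Not stated |
| Where is the pairing described? | Protocol 2.6.3 only | 4 sites; in the intervention group also 2 sessions × 3 periods |
| Does the SAP supply it? | SAP 2.3 | No; only independent-sample tests are named for numerical data |
| Who checks the method? | SAP 1.1 | Research managers; no time and no masking stated |

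**Inputs for the illustration.** n = 40 people per group (protocol 2.1 and 2.4). Significance level 0.05 (SAP 2.3), taken as two-sided because sidedness is not stated. Within-person correlation ρ = 0.3, 0.5 or 0.8 is an assumption; the documents give no value.

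**Loss of power when paired records are tested as unpaired.** A paired t test in 40 people has 80% power at a standardised mean difference dz = 0.454 (mean difference divided by the SD of the differences). In units of the between-person SD that effect is dz × √(2(1−ρ)) = 0.537, 0.454 or 0.287.

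The independent t test (78 degrees of freedom, critical value 1.991) overstates the variance of the difference, by a factor of 1/(1−ρ). Its approximate power is Φ(dz√40 − 1.991/√(1−ρ)), with dz√40 = 2.871:

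- ρ = 0.3: Φ(2.871 − 2.380) = Φ(0.49) = 69%
- ρ = 0.5: Φ(2.871 − 2.816) = Φ(0.06) = 52%
- ρ = 0.8: Φ(2.871 − 4.452) = Φ(−1.58) = 6%

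Simulation (40,000 datasets of 40 pairs), which also allows for the estimated variance, gives 69%, 53% and 8%. At ρ = 0 there is no loss.

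**Type I error of the same misuse.** 2(1−Φ(1.96/√(1−ρ))) gives about 1.9%, 0.6% and below 0.1%. The unpaired test on within-person data is conservative, so the error here is towards a false negative.

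**Pooling both sessions as if from different people.** Take 80 intervention records against 40 controls. The true variance of the difference is σ²[(1+ρ)/80 + 1/40] = σ²(3+ρ)/80. The test assumes 3σ²/80, so the ratio is 1 + ρ/3. Type I error is 2(1−Φ(1.96/√(1+ρ/3))) = 6.2%, 7.0% and 8.2%, against a nominal 5%.

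**The case against.** The strongest reply is that the sentence in 2.5 is loose wording for an ordinary masked analysis. The sentence before it promises blinded analysis, the SAP says only that the statistician is blinded, and the literal reading is awkward: the SAP is Part 3 of the same document, so an analyst kept from all of it could not see which tests to run. This may well be what was meant. It does not remove the point, because no section says that groups are coded, and the one definition given names a different object.

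A reader might infer that the analyst cannot know which records are paired. The documents do not support that. They do not describe the analysis file, which could carry participant, session, site and period columns. What stands is that nothing in the plan requires those columns.

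A reader might also blame a wrong test on the blinding sentence. Most of that risk comes from SAP 2.3: a fully informed analyst who followed it would use the same unpaired test. The check by research managers in SAP 1.1 is a real safeguard, since they are not described as kept from the protocol and could notice an unpaired test. It is only partial, because no time is set for it.

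Finally, a reader might claim inflation to 8.6%, 11.0% or 14.4% from 2(1−Φ(1.96/√(1+ρ))). That formula fits a one-sample test, or two groups that both have two sessions. Here only the intervention group has two sessions, and the unpaired within-person test is conservative.

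**Conclusion.** The point holds in a limited form. The rule in 2.5 masks the wrong thing: it leaves COPD and control identity open and does not assure the analyst of the design information. It should be corrected before analysis, but it does not by itself invalidate any result. The COPD-versus-control comparison at a single site has one recording per person, so the pairing problem does not touch it; that comparison lacks only the masking.

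For within-person comparisons, an unpaired test would cut 80% power to about 69%, 53% or 8% at ρ = 0.3, 0.5 or 0.8. Pooling 80 intervention records against 40 controls would raise type I error to about 6%, 7% or 8%. Both sets of figures rest on assumed correlations and show what a wrong test would cost. Neither is a certain consequence of the blinding sentence.

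**What to change.** 1. Replace the defining sentence in protocol 2.5. Statisticians receive the full protocol and SAP and are masked to group identity. COPD and healthy control are supplied as codes A and B, and the codes are broken only after the analysis program is final.
2. State that the data file carries participant, session, site and period identifiers for every record.
3. State that the moxibustion group cannot be masked: its two sessions, its midpoint sites and its 25-minute recordings (5 + 15 + 5) identify it.
4. In SAP 2.3, name a paired or repeated-measures (mixed-model) method for within-person comparisons and keep the independent-sample test for COPD against control at a single site. The edit to 2.5 alone does not correct the test.

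The cost is one paragraph in 2.5, a few lines in SAP 2.3 and a coded group variable. There is one small downside: the analyst of the moxibustion data will know the hypothesis and which site was heated. That is acceptable, because those data cannot be analysed properly without knowing their structure.
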